#### **5.5 Lost to Follow-up**

A participant will be considered lost to follow-up if the study site is unable to contact him/her. In case of missed phone contact, the investigator or designee must make every effort to reach the participant (i.e., three phone calls). Should the participant continue to be unreachable up to 14 days after the scheduled phone follow-up visit (V2), after at least three contact attempts, he/she will be considered to have withdrawn from the study.

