#### Safety (Timeframe: day 1 to day 7)

To validate the safety of Endorail in long-lasting, colonoscopies by demonstrating that colonoscopy serious adverse events are not increased using the device (i.e., in particular the absence of device-related serious adverse events).

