## 3. STUDY ENDPOINTS

### 3.1 Primary Endpoints:

Efficacy:

The primary efficacy endpoint is the percentage minor or equal to 10% of incomplete long-lasting colonoscopies (colonoscopy is defined completed when caecal intubation is achieved)

AND

Safety:

Medical adverse events and medical device adverse events will be collected during the study.

The primary safety endpoints are:

The absence of device-related serious adverse events.

AND

The evaluation of the equality or reduction of the adverse events rates compared to diagnostic colonoscopies without Endorail.

The adverse events assessed are:

- Occurrence of general adverse events and medical device incidents;
- Occurrence of specific adverse events: gastrointestinal bleedings, intestinal perforation, mucosal petechiae and abdominal pain.

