#### **4.7 Replacements**

Patients who withdraw the informed consent before the completion of the procedure can be replaced by newly recruited patients. Similarly, for patients who are found to be lost to follow-up following the procedure completion and therefore cannot be reached by phone for the scheduled follow-up visit (Visit 2) a second and third attempt should be made after the second and third week; if the patient is still untraceable it can also be replaced by newly recruited patients (See section 5.5).

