#### 5.3.2 Compliance with study intervention

Each enrolled patient will be contacted by telephone (V2, see **Section 6.2.2**) 7 days after the procedure to evaluate the occurrence of general and specific adverse events from the previous visit. To improve the adherence to the follow up, the investigator will recommend the commitment of each participant in concluding the study schedule.

In case the patient does not respond at the scheduled phone visit, a second attempt should be tried one week after V2 and, in case he/she is still untraceable, he/she will be re-contacted two weeks

---

after V2. In case the contact is still unsuccessful, the patient will be defined as lost to follow up as indicated in Section 5.5.

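### Only phone calls are required before an unreachable patient is closed as withdrawn, so a serious event after discharge could escape a safety endpoint that one event would fail

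*Combined protocol and SAP*

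**What the plan says.** Section 3.1 makes one primary safety endpoint a zero-event criterion: "The absence of device-related serious adverse events". Section 2.1 sets the window: "Safety (Timeframe: day 1 to day 7").

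Visit 2, a phone call on Day 7 ± 1, is the only scheduled contact after discharge (Table 1, section 6.2.2). If it fails, section 5.3.2 says "a second attempt should be tried one week after V2", with a last attempt two weeks after Visit 2. It then states: "In case the contact is still unsuccessful, the patient will be defined as lost to follow up as indicated in Section 5.5".

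Section 5.5 spells out the effort in terms of phone calls only: "the investigator or designee must make every effort to reach the participant (i.e., three phone calls"). A patient unreachable up to 14 days after Visit 2 is then closed: "after at least three contact attempts, he/she will be considered to have withdrawn from the study". Section 4.7 adds that "if the patient is still untraceable it can also be replaced by newly recruited patients".

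Other sections bear on the point:

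- Section 6.2.1 records intra-procedure events, and events from consent to discharge, at Visit 1.
- Section 7.2 collects spontaneous reports, observations and answers to open questions.
- Section 7.2.4 requires SAEs to be reported within 24 hours of awareness.
- Section 7.3 keeps recording open after the last contact for device-related SAEs that the investigator learns of.
- Section 8.4.1 defines ITT as everyone who started Endorail, whether or not Visit 2 took place.
- Section 8.5 gives no rule for missing data beyond leaving it unfilled.

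**The concern.** Failure to answer the phone may carry information about safety. Death and hospitalisation are SAE criteria in section 7.1.1, and both are reasons why a call goes unanswered. Section 4.5 requires the reason and date of any death to be recorded, but no procedure would let the site learn of a death behind unanswered calls.

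The endpoint has no tolerance, since a single device-related SAE turns success into failure. If patients with late complications are more likely to be lost, the error runs towards success. The plan also does not say how an unreached patient counts. Section 4.7 and the drop-out allowance in section 8.2 suggest replacement or discard, while the ITT definition in section 8.4.1 suggests retention.

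**Working it through.** **Step 1: the plan's figures.** Section 8.2 uses p0 = 20%, p1 = 10.1%, α = 5% and power 80%, and section 8.4 makes the test one-tailed. With the normal approximation:

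n = [(1.645·√(0.20·0.80) + 0.842·√(0.101·0.899)) / (0.20 − 0.101)]² = 84.8, so 85.

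Then 85/0.90 = 94.4, so 95. Both figures reproduce. The allowance is 95 − 85 = 10 patients. Section 8.2 applies it to discarded cases as well as losses to follow-up, so 10 is the most losses the allowance would cover, not a forecast.

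**Step 2: which events can be missed.**

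| When | How an event is captured | If the patient is never reached |
|---|---|---|
| Procedure to discharge | Recorded at Visit 1 for all treated (6.2.1) | Still captured |
| Discharge to Day 7 | Visit 2 call, repeated at about Days 14 and 21 (7 + 7 and 7 + 14) | Captured only if the site hears by another route (7.2, 7.2.4, 7.3) |

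Only the second row is exposed. Nothing there tells the site to look for the event. Section 6.1.2 asks for safety information when a withdrawal is communicated, and section 5.4 covers patients who withdraw consent. An unreachable patient does neither.

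**Step 3: loss unrelated to outcome.** With zero events in n patients, the one-sided 95% upper bound is 1 − 0.05^(1/n).

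- n = 95: 3.1%
- n = 85: 3.5%

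Ten random losses cost 0.4 percentage points.

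**Step 4: loss caused by the event.** If one unreached patient had a device-related SAE, the true result is 1/95. The endpoint fails, and the exact one-sided 95% upper bound is 4.9% instead of 3.1%.

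Let q be the rate of device-related SAEs arising after discharge, and r the share of those patients who are never reached and not otherwise reported. The chance of seeing no event in 95 patients is (1 − q(1 − r))^95.

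| q | r = 0 | r = 10% | r = 50% | r = 90% |
|---|---|---|---|---|
| 0.068% | 94% | 94% | 97% | 99% |
| 1% (assumed) | 38% | 42% | 62% | 91% |
| 2% (assumed) | 15% | 18% | 38% | 83% |

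The 0.068% is the only serious-event figure in the documents: (47 + 4 + 7 + 10)/100,000 in section 8.2. It refers to screening or surveillance colonoscopy, is not device-specific and may be low for long-lasting procedures. The 1% and 2% rates and every value of r above zero are assumptions.

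**The case against.** A reader might infer that the safety endpoint is judged on reachable patients only, or that ascertainment stops once a patient is closed. The documents support neither. Visit 1 covers every treated patient up to discharge, ITT does not depend on Visit 2, and sections 7.2.4 and 7.3 still require an SAE to be reported or recorded when it becomes known (after the last contact, if device-related).

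The hospital scenario is also narrower than it first appears. The patient must miss at least three attempts over about two weeks, and the site must hear nothing by any other route. A call answered around Day 21 would still reveal a Day 1–7 event. A short admission would probably come to light; a death or a prolonged stay might not.

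A reader might also take the larger shifts in the table as the expected bias. They rest on assumed rates. At 0.068%, missing half the events moves the chance of a clean result by about 3 points.

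Finally, how far to trace a patient is partly a matter of judgement. Section 9.1.2 requires current medical records to be available, and section 9.3 has monitors check communications with family doctors, if any.

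These arguments limit the size of the problem but do not remove it. The passive routes depend on someone contacting the site, and sections 9.1.2 and 9.3 concern source documents and monitoring, not tracing before closure. The absence of any rule for counting unreached patients also stands.

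**Conclusion.** The point holds as a limited gap that is cheap to close. A device-related SAE arising after discharge in a patient who is never reached could go unseen, and the zero-event endpoint could then be declared met. If loss is unrelated to outcome, the cost is a change in the upper bound from 3.1% to 3.5%, even if the whole allowance of 10 is lost. If the event causes the loss, one hidden case reverses the endpoint. How likely that is cannot be derived from the documents: missing half the events adds about 3 points to the chance of a clean result at 0.068%, and about 24 points at an assumed 1% (38% to 62%). The plan does not show that such bias will occur; it lacks a step that would rule it out.

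**What to change.** **Section 5.5.** After three failed calls, require a check of the site's own admission and emergency records. Where consent allows, add a contact with the family doctor or a contact person named by the patient. Limit both to vital status and hospitalisation up to Day 7. Class the patient as lost only after this.

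**Sections 8.4.1 and 8.5.** Keep every patient who started Endorail in the ITT safety denominator, including those replaced under section 4.7. If 10 were replaced, the denominator would be 95 + 10 = 105. Report the number without Day 7 status beside the endpoint. Add a worst-case sensitivity line counting those patients as events.

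The worst-case line should be a sensitivity display for safety, not a decision rule. Any unreached patient makes it non-zero. Applied to the composite test at n = 95, where the exact one-sided test allows at most 12 events, 10 losses counted as events would leave room for 2 among the other 85. The chance of that at the planned 10.1% rate is 0.7%.

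**Cost.** A few sentences, and a record check for at most about 10 patients if losses stay within the allowance. The further contact may need a consent-form change, which requires sponsor and ethics committee approval (section 9.6.1), in a trial run in three countries. The consent form was not available to me, so such contact may already be permitted. The record check should be feasible even if the consent form stays as it is, subject to local rules. The safety result may become less favourable.

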#### **5.6 Trial specific preventive measures**

No specific preventive measures other than those indicated in the exclusion criteria (Section 4.3) are foreseen.

#### **5.7 Concomitant Interventions (treatments)**

##### **5.7.1 Permitted Medicines**

Participants will be allowed to use any concomitant medication necessary for the treatment of pre-existing concomitant pathologies or for intercurrent diseases, provided that they do not interfere with the parameters under investigation.

As anticipated in Section 5.2.1, sedation will be performed by an anaesthesiologist or an endoscopist according to standard of care.

### **5.7.2 Prohibited Medicines**

No prohibited concomitant treatments are currently defined.

### **5.7.3 Other Interventions**

The patient preparation to colonoscopy will be performed according to standard practice used in the investigational study site.

#### **5.7.3.1 Special Precautions**

Not applicable. No special precautions other than those detailed in Section 5.2 will be implemented.

#### **5.7.3.2 Management of Specific Adverse Events or Adverse Medical Device Reactions**

Specific adverse events will include gastrointestinal bleedings, mucosal petechiae, intestinal perforation and abdominal pain. However, these specific adverse events are general potential adverse events that might occur during colonoscopy. No specific adverse events (AEs) or adverse device effects (ADEs) are described with the use of the investigational product due to the low risks associated with the medical device under study.

#### **5.7.3.3 Medical Care of Subjects after End of Trial**

No specific requirements for medical care of subjects after the end of the trial will be implemented.

### **5.8 Medical Device Accountability**

After receipt of the investigational products supplies, the Principal Investigator or his deputy will conduct an inventory and subsequently fill-in and sign the investigational product Delivery Form called “Device Accountability Log”. The Principal Investigator or his deputy, will keep an investigational product inventory and accountability records.

The Principal Investigator will keep the investigational products in a locked and secure storage facility, accessible only to those individuals authorised by the Principal Investigator himself.

### **5.9 Return or Destruction of Medical Device**

At the conclusion of the study, a final investigational product inventory will be performed, and the unused investigational products will be returned to the Sponsor together with an investigational product Return Form accurately filled-in and signed by the Principal Investigator or his deputy. If any supplies are missing, this must be specified within the Return Form together with an explanation for the discrepancy.

## 6. STUDY ASSESSMENTS

### 6.1 Assessments of Endpoints

The primary endpoint is the evaluation of the efficacy and safety of Endorail in patients undergoing long-lasting colonoscopies.

#### 6.1.1 Assessment of primary Endpoints

The efficacy endpoint is measured at V1 as the successful completion of the long-lasting colonoscopy (Colonoscopy completion is defined as the caecal intubation).

The safety endpoint is evaluated throughout the entire study duration by collecting the medical adverse events and the medical device adverse events.

#### Adverse events

Definitions, coding, methods of collection of adverse events and medical device incidents are described in detail in Section 7.1.1. Special attention will be given to the following specific adverse events: gastrointestinal bleedings, intestinal perforation, mucosal petechiae and abdominal pain.

#### Vital signs

The following vital signs will be assessed before and after the procedure (Section 5.2):

- Blood pressure and heart rate will be measured before the procedure;
- Blood pressure and heart rate will be measured at approximately 30 minutes after completing the procedure.

#### 6.1.2 Assessments in participants who prematurely stop the study

Considering the brevity of the follow up period, at the moment of the withdrawn communication the patient will be asked for safety information about the concomitant treatments and the occurrence of any adverse event.

### 6.2 Procedures at each visit

The study plan scheduled examinations and procedures are summarised in Table 1. The study plan will include a screening/ treatment visit (Visit 1 - Day 1), during which the colonoscopy with the investigational medical device Endorail will be performed. A phone follow-up visit (Visit 2) will be scheduled 7 ( $\pm$  1) days after treatment with the investigational medical device Endorail.

#### 6.2.1 Treatment Visit - Visit 1 (Day 1)

Potential participant patients, prospectively attending the investigational study to undergo colonoscopy, will be informed, orally and in writing, about the scope of the study, the relevant procedures, the nature of the risks related to the study, and they will be asked to sign and date the written Informed Consent Form.

After the correct obtaining of the Informed Consent, the following assessments and procedures will be performed during Visit 1 (Day 1):

- Demographic data (age, sex, race) will be recorded;
- A detailed medical history, with special attention to previous history of diverticular disease, hysterectomy, gastrointestinal surgery, implantable devices will be recorded in the patient's medical record and in the appropriate section of the eCRF;
- All concomitant medications being taken by the patient, including treatments administered in the last 4 weeks, will be checked and will be recorded in the patient's medical records and in the appropriate section of the eCRF;
- A general physical examination will be performed. The physical examination will include an examination of head, ears, eyes, nose, mouth, skin, heart, and lung examinations, lymph nodes, genitourinary, gastrointestinal, skeletal, and neurological systems. Any identified abnormality should be recorded in the patient's medical records and in the eCRF;
- Height, weight, BMI;
- Vital signs (blood pressure, heart rate) will be measured and will be recorded both in the patient's medical record and in the appropriate section of the eCRF;
- Inclusion/exclusion criteria will be reviewed and eligible patients will be included in the study;
- Pre-procedure sedation will be performed according to the standard of care;
- Procedure for colonoscopy will be started;
- Caecal intubation time will be recorded;
- Colonoscopy will be performed and completed according to procedures detailed in Section 5.2.;
- In case caecal intubation time is longer than 10 minutes, the patients can be enrolled.
- The occurrence of local (intra-procedure) adverse events (i.e. gastrointestinal bleeding, intestinal perforation, presence of mucosal petechiae and abdominal pain) will be checked and (if any) will be recorded in the patient's medical records and in the appropriate section of the eCRF;
- At the end of the colonoscopy, successful or failed caecal intubation will be recorded in the patient's medical record and in the appropriate section of the eCRF;
- Vital signs (blood pressure and heart rate,) will be measured approximately 30 minutes after completing the procedure and will be recorded in the patient's medical record and in the appropriate section of the eCRF;
- The occurrence of general and specific adverse events from obtainment of Informed Consent Form will be checked and (if any) will be recorded in the patient's medical records and in the appropriate section of the eCRF;
- Patient will be discharged and an appointment will be taken for the phone follow-up visit, scheduled after 7 ( $\pm$  1) days from the procedure.

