#### **4.4 Recruitment and screening**

Before starting the recruitment, each investigator must be familiar with the device under investigation.

If the Investigator has never used the Endorail device, he/she should perform at least three colonoscopy procedures with Endorail. To assess the performance case, the Investigator should sign a self-declaration titled “Performance case declaration” stating that the three cases have been duly performed in compliance with Protocol requirement.

Before any screening procedure all patients must sign a written informed consent for the study. The following logs must be maintained at each study site and kept in the Investigator Site File: a “Subject Screening Log\Enrolment Log”, to document the identification of subjects who enter screening and to document chronological enrolment of patients, a “Subject Identification List” for all subjects registered to maintain the correlation with the patient's full identification data (name, surname - confidential).

Eligible patients who have provided written informed consent to study participation and that satisfy all inclusion criteria and none of the exclusion criteria both detailed in Section 4.3, will be enrolled in the clinical study.

Eligibility will be determined by the investigator basing on standard colonoscopy clinical history and colonoscopy indication. Enrolment will be completed during colonoscopy if caecal intubation time is longer than 10 min.

When the investigator registers in the eCRF the enrolment of a new patient, the eCRF will assign a 4-digit identification number to each patient included in the investigation. The patient number will be sequentially assigned to each patient who signs the informed consent, starting from 0001. If a subject discontinues from the study, the patient number will not be re-used, and the subject will not be allowed to re-enter the study. Moreover, to distinguish the patient number of different sites involved in the clinical trial, the 4 digit patient number will be preceded by a 2-digit site number. Before the study initiation, the Sponsor will assign to each participating site its unique 2-digit site number.

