#### **8.4.1 Datasets to be analysed, analysis populations**

- Screening set: will include all patients who have signed the informed consent and have been screened for inclusion in the study;
- Intention-to-treat population (ITT): will include all enrolled patients who have started treatment with Endorail;
- Per-Protocol (PP) population: will include all patients of the ITT who also meet all inclusion/exclusion criteria and who do not have any major protocol deviation, to be defined in a data review meeting (DRM) of the Sponsor, Contract research Organization (CRO) representatives and the biostatistician.

Analysis will be performed on the ITT population and will be repeated in the PP population. The results obtained in the PP population will be seen as confirmative of those observed in the ITT population.

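### Sections 4.4 and 6.2.1 conflict on when and whether a long-lasting case is enrolled, and no section fixes enrolment before Endorail is inserted or the outcome is visible

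*Combined protocol and SAP*

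**What the plan says.** **Timing and obligation.** Section 4.4 states that consented patients who meet the criteria will be enrolled, and adds: "Enrolment will be completed during colonoscopy if caecal intubation time is longer than 10 min". The Visit 1 list in section 6.2.1 has "Colonoscopy will be performed and completed according to procedures detailed in Section 5.2", and the next item reads "In case caecal intubation time is longer than 10 minutes, the patients can be enrolled". Two items further on: "At the end of the colonoscopy, successful or failed caecal intubation will be recorded".

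**Patient number.** Section 4.4 says "When the investigator registers in the eCRF the enrolment of a new patient, the eCRF will assign a 4-digit identification number". The following sentence says "The patient number will be sequentially assigned to each patient who signs the informed consent, starting from 0001". The synopsis (Measurements and procedures) expects about 80% of those who sign consent not to be enrolled, because their procedure is not long-lasting.

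**Analysis set.** Under section 8.4.1 the ITT population "will include all enrolled patients who have started treatment with Endorail". The main analysis is on this set.

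**Design.** Section 4.1 describes a single-arm, open-label study. The endpoint is caecal intubation, which the operator observes directly.

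**The concern.** Which cases enter the ITT set depends on enrolment, so the moment of enrolment matters. In a single-arm trial tested against a fixed 20% there is no concurrent arm in which selective inclusion would cancel out. If enrolment can be registered after the operator has seen whether the caecum was reached, leaving out a few failures lowers the recorded incompletion rate without any device effect. The bias measures in section 4.2 (training, sample size, several centres) do not address this.

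The two numbering triggers add to the problem. Numbers issued at consent would give an unbroken sequence in which every consented patient must be accounted for. Numbers issued at registration of enrolment would not. With about 80% of consenting patients not expected to be enrolled, the two rules describe very different sets, and sites may follow either.

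**Working it through.** **1. The passages side by side**

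| Question | Section 4.4 | Section 6.2.1 |
|---|---|---|
| Is enrolment of an eligible case required? | Yes | Worded as a possibility |
| When? | During the colonoscopy, no point named | Listed after the item on completing the colonoscopy, before the item recording success or failure |
| When is the number issued? | At registration of enrolment, and also at consent | Not stated |

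Neither section names minute 10, opening of the Set or balloon insertion as the latest time for enrolment. The timing in 4.4 does not settle it, since the caecum can be reached or the attempt abandoned while the colonoscopy is still under way. Both sections also tie enrolment to the caecal intubation time, which read literally exists only once the caecum is reached. Inclusion criterion 2 in section 4.3 (caecum not reached after 10 minutes) is the version that can be applied in advance.

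**2. The plan's own figure**

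Inputs from sections 8.2 and 8.4: p0 = 0.20, p1 = 0.101, one-sided alpha 0.05, power 0.80.

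n = [(1.645 × √(0.20 × 0.80) + 0.842 × √(0.101 × 0.899)) / (0.20 − 0.101)]² = 84.8, so 85. With 10% drop-out, 85/0.90 = 94.4, so 95. Both figures reproduce.

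**3. Success boundary under the exact binomial test of section 8.4**

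- n = 85: success if at most 10 events; P(X ≤ 10 | 0.20) = 3.3%.
- n = 95: success if at most 12 events; P(X ≤ 12 | 0.20) = 4.2%.

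**4. Illustration of unregistered failures**

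Let the true event rate be 20%, and let a share f of failures go unregistered. A failure here is an event on the merged indicator of section 8.2. At that section's adverse event rate of 0.068%, nearly all failures are incomplete procedures. The registered rate is

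r(f) = 0.2(1 − f) / (1 − 0.2f).

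For example, f = 0.10 gives 0.18/0.98 = 18.4%. The expected number left out for n registered patients is n × 0.2f / (1 − 0.2f); for n = 85 and f = 0.10 this is 85 × 0.02/0.98 = 1.7.

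| f (assumed) | Registered rate | Left out, n=85 | False success, n=85 | Left out, n=95 | False success, n=95 |
|---|---|---|---|---|---|
| 0 | 20.0% | 0 | 3.3% | 0 | 4.2% |
| 5% | 19.2% | 0.9 | 4.9% | 1.0 | 6.3% |
| 10% | 18.4% | 1.7 | 7.1% | 1.9 | 9.1% |
| 20% | 16.7% | 3.5 | 14.1% | 4.0 | 18.1% |

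The documents give no rate of non-registration, so f is an assumption throughout. The figures are for one final test and leave out the interim looks of section 8.4.2.

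**The case against.** The strongest reply is that the plan does not permit selection. Section 4.4 makes enrolment of eligible patients mandatory, and the synopsis equates being enrolled with Endorail being used after 10 minutes. Leaving out a patient in whom Endorail was used and failed would breach the protocol. This stands, and it rules out reading the plan as making enrolment optional. What remains is that 6.2.1 words the same step differently and that no enrolment time is required, so such a breach has no explicit check.

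A reader might infer from 6.2.1 that enrolment follows the outcome. The documents do not support that. The list is not strictly chronological: intubation time comes before the completion item and intra-procedure adverse events come after it. The enrolment item also precedes the one recording success or failure.

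A reader might add that the operator cannot use the eCRF during the procedure. No section says so, and section 9.1.1 gives data collection to centre staff under the Principal Investigator.

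A reader might conclude that an omitted case would be invisible. That is too strong. Traces would include the chronological screening/enrolment log (4.4), the Screening set (8.4.1), user and time stamps (9.2.2), monitoring (9.3) and device accountability records (5.8). However, the stamps mark data entry rather than the clinical event, video is made only if possible (5.2.1), and no section requires used Sets to be matched to analysed patients.

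Finally, the assumed shares are hypothetical, and any binary test can turn on one case at its boundary. Both points are fair. The table shows sensitivity and is not an estimate of bias.

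**Conclusion.** The conflict between 4.4 and 6.2.1 is real, as are the double trigger for the patient number and the lack of any fixed enrolment point before device use. Because the ITT set depends on enrolment, the text leaves room for outcome-dependent inclusion in a design where the operator sees the endpoint. It does not show that selection occurred or that the plan allows it.

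The size depends on an unknown share. If the true rate is 20%, non-registration of 5% to 10% of failures, about one or two patients, takes the single-look error to between 4.9% and 7.1% at n=85 and between 6.3% and 9.1% at n=95. At 20% it is 14.1% and 18.1%. The sample size of 85, or 95 with drop-out, is unaffected. The change should be made because the guard is cheap and the sections need reconciling in any case.

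**What to change.** 1. **Section 4.4.** Assign the patient number to every patient at consent and delete the sentence that ties it to registering enrolment.
2. **Section 6.2.1.** Place enrolment before Endorail use. State that every consented patient without caecal intubation at 10 minutes who meets all inclusion and no exclusion criteria, including exclusions seen only at endoscopy (such as bowel preparation, strictures or fixed curves), will be enrolled. Log the reason for any such patient not enrolled. Record the clock time of enrolment before the Endorail Set is opened.
3. **Sections 5.8 and 8.4.1.** Before each interim and the final analysis, reconcile the used Sets in the Device Accountability Log with ITT patients. Explain each unmatched Set: a training case under 4.4, a replacement after malfunction under 7.2.4, or a withdrawal with data deletion under 5.4. Include in the ITT set, with the actual outcome, any other consented patient in whom Endorail was started.

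Restricting item 2 to eligible patients matters, because a bare requirement to enrol every case over 10 minutes would bring in patients excluded on endoscopic findings. The explanations in item 3 matter too, because counting every unmatched Set would contradict the data deletion right in 5.4.

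The cost is an amendment to the wording, one clock time noted during the procedure, and a short reconciliation against a log already kept. Sample size and treatment do not change.
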